1.0 Study Summary

Study Title	BRITEPath-ETUDES Phase 1b
Study Design	Stepped wedge randomization; We will evaluate BRITEPath’s feasibility and efficacy compared to treatment as usual care (TAU) across sites.
Primary Objective	We will create and rapidly iterate user interfaces to develop the three components of BRITEPath: (1.) Guide2BRITE, an electronic guide for mental health clinicians providing step-by-step instructions in the onboarding of the safety plan, emotion regulation, and distress tolerance skills for (2.) the BRITE app, a personalized and interactive safety plan and self-monitoring tool for the adolescent; and (3.) the clinician dashboard, BRITEBoard, to track adolescents’ app use, distress, and treatment progress as well as to promote communication and collaboration among mental health and primary care providers.
Secondary Objective(s)	We will test BRITEPath's impact compared to TAU utilizing a stepped wedge design and a RE-AIM framework. BRITEPath focuses on novel approaches to support treatment and management of adolescent depression and suicidality in pediatric primary care and community mental health settings.
Research Intervention(s)/ Investigational Agent(s)	Mobile App based intervention
IND/IDE #	n/a
Study Population	12-26 yo patients seeking mental health treatment
Sample Size	50
Study Duration for individual participants	12 weeks
Study Specific Abbreviations/ Definitions	BRITEPath=BP Guide2BRITE=G2B BRITE=app used on participant Mental health=MH Behavioral health=BH

2.0 Objectives*

Suicide and suicidal behavior are leading causes of adolescent mortality and morbidity. Suicide ideation is one of the strongest predictors of imminent suicide or suicide attempt. Among common psychiatric disorders, depression has the strongest association with suicide ideation and attempt, but anxiety, substance abuse, and disruptive disorders also elevate risk. Therefore, to identify adolescents at high suicidal risk, it makes sense to screen for depression AND for suicidal ideation, regardless of diagnosis. There is some evidence, mostly in adults, that brief interventions can reduce risk for suicidal behavior, whether through improved connection with services, increased sense of connection and social support, or via systematic follow-up, and while some brief interventions aimed at safety planning have been advanced, there are no brief interventions for adolescents. Furthermore, insufficient resources are available to guide clinicians in suicide risk assessment and management. In fact, a review of the literature for suicide prevention apps shows that of 123 available smartphone apps, none are geared to providing guidance for clinicians treating adolescents. This lack of resources is especially problematic because as primary care clinics implement depression screening for adolescents and enhance collaborative mental health (MH) care as recommended by the United States Preventive Services Task Force (USPSTF), more youth with depression AND those with acute suicide risk will be identified. Adolescents receiving treatment from an embedded MH provider may also result in the identification of even more adolescents with acute suicide risk. Enhancing mental health screening and providing embedded mental health treatment in primary care may have the unintended negative consequence of increasing emergency referrals and hospitalizations, which reflect the absence of current suicide risk management practices in primary care. Emergency department (ED) referrals for further evaluation are among those least favored by suicidal patients and may inadvertently decrease patients' motivation to access and engage in follow-up treatment. Thus, there is urgent need to equip primary care with the capacity to assess and stabilize depressed and suicidal adolescents, in order to avoid unnecessary ED referrals and hospitalizations and ultimately, to reduce suicidal behavior upon follow-up.

We will develop an app-based intervention, BRITEPath that enhances the capacity of pediatric primary care to effectively manage depressed and suicidal adolescents by referral to embedded MH services. BRITEPath includes three components delivered by MH clinicians, including (1.) an electronic on-boarding procedure tool that supports MH clinicians, Guide2Brite; (2.) the adolescents' safety planning app, BRITE; and (3.) the clinician dashboard, BRITEBoard, to facilitate treatment planning and communication with other primary care providers.

2.2 The aims and hypotheses related to this specific protocol and submission are below for Phase 1b. Aims of the previous phase are in a University of Pittsburgh OSIRIS IRB protocol submission (#PRO18050281) entitled ETUDES Phase 1a-qualitative. Aims of later phases described briefly will be submitted in subsequent protocols.

PROTOCOL TITLE: The Center for Enhancing Treatment & Utilization for Depression and Emergent Suicidality Phase 1b-Study 3-BRITEPath

We will test the feasibility of using BRITEPath in community & pediatric practices using a stepped wedge design. We hypothesize that participants, parents, and clinicians will find the intervention usable and feasible to deploy. We will assess the impact of BRITEPath alone (compared to its impact as part of iCHART in later phases of the ETUDES Center, by obtaining follow-up phone assessments on suicidality, depression, and functional status at 4 and 12 weeks after intake.

Aim 1b (Phase 1b, Feasibility). We will pilot BRITEPath in sites using a stepped wedge design (50 adolescents aged 12-26 yo). Hypothesis 1b: The use of BRITEPath will decrease depressive symptoms, distress, and suicidality (any self-injurious ideation, urges, or behavior) as well as improve overall functioning compared to TAU.

Criterion for success: 75% of adolescents who receive BRITEPath will use it, and 75% of MH clinicians will use Guide2BRITE and BRITEBoard.

3.0 Background*

Drs. [name] (PI) and [name] (Co-PI) have expertise with all aspects of the proposed study: developing psychosocial interventions targeting suicide, partnering with private companies to create smartphone apps to monitor suicide and other high risk behaviors in daily life as well as analyzing the intensive longitudinal data resulting from such research protocols, conducting randomized controlled trials of psychosocial interventions for suicidal adolescents, and evaluating long-term outcomes from longitudinal studies of high risk adolescents and families with excellent retention.

In a previous study, [name] and colleagues developed a brief, inpatient-based, novel intervention with an accompanying safety planning app (BRITE) for psychiatrically hospitalized, suicidal adolescents. In a pilot RCT with 66 adolescents, this app-supported intervention cut the incidence of recurrent suicide attempts by half (Incidence rate ratio [IRR] for attempts=0.47, 95%CI 0.12-1.56, $p=0.18$), with a stronger effect in the 80% of adolescents with a previous history of a suicide attempt (IRR=0.23, 95% CI, 0.05-1.09). The app was accessed an average of 29 times over a 6-month period, 45.5% accessed the safety plan, and the more frequently the app was used, the greater the decline in suicidal ideation and increase in reasons for living ($\rho=0.36$, $p's=0.08$). Participants rated BRITE high on usability using the Post-Study Satisfaction and Usability Questionnaire (lower score indicates greater satisfaction, range 10-70, mean scores 17.6-18.4). Moreover, clinicians who implanted the interventions wanted the app to guide them in formulating the safety plan and populating the app for use by the adolescent. These data provide preliminary support for the clinical utility of an app-supported intervention to reduce suicide risk in adolescents. An important next step is to further develop BRITE for use in pediatric care clinics by

PROTOCOL TITLE: The Center for Enhancing Treatment & Utilization for Depression and Emergent Suicidality Phase 1b-Study 3-BRITEPath

developing a virtual treatment manual designed to guide clinicians in delivering the intervention and a clinician dashboard to monitor symptoms and treatment progress.

4.0 Study Endpoints*

At anytime, the primary investigators may discontinue a participant's participation in this study. The PI may decide to remove a participant off this study if their health or safety may be at risk; if they have not been following study instructions or because of a study administrative decision by the PI.

5.0 Study Intervention/Investigational Agent

Overview of the BRITEPath intervention

There are three components of the BRITEPath intervention, each of which will be described: 1) BRITE, 2) GUIDE2BRITE and 3) BRITEBoard. All participants assigned to the intervention components will receive each of these 3 components.

BRITE

BRITE is a tool for self-monitoring and self-management that is not targeting any specific diagnosis or medical condition. BRITE includes monitoring of distress on a daily basis paired with content targeting skill targeting emotion regulation, distress tolerance, social support, and reasons for living. Content will take the form of clinician-recommended videos, photos, and websites, as well as personalized content that has salience to the adolescent that they may add onto their app. In this way, the app is customizable to uniquely meet the adolescents' needs and preferences. Adolescents will be encouraged to use the skills on the app on a daily basis. Additionally, the BRITE app will include an electronic version of a safety plan that will be developed in collaboration with the youth's therapist. Safety plans, which contain coping strategies, social supports, and crisis contacts are used as a standard of care in the treatment of suicidal youth. Finally, on each screen of the app, there is a link to crisis contacts that will be programmed onto the app with the assistance of their therapist.

GUIDE2BRITE

Embedded mental health providers, who will treat youth who have access to the BRITE app, will use GUIDE2BRITE to facilitate the process of orienting youth to the app. GUIDE2BRITE will be an interactive website that leads the clinician through the process of developing a safety plan and identifying appropriate content for the BRITE app with their adolescent patient. During this process, providers will orient patients on the purpose and function of the app, demonstrating and practicing skills they will use as part of the app-based intervention. Guide2BRITE supports clinicians in the delivery of an intervention designed to: (a) identify likely triggers of suicidal and self-harm urges; assess lethality and restricting access to means; (b) teach skills via modeling and role-play to cope with suicidal and self-harm urges and (c) identify professional resources to access in a crisis should others means of coping fail. A mock-up that

PROTOCOL TITLE: The Center for Enhancing Treatment & Utilization for Depression and Emergent Suicidality Phase 1b-Study 3-BRITEPath

shows the integration between BRITE and GUIDE2BRITE is provided within question 2.

BRITEBOARD

BRITEBOARD is a web-based portal that tracks participants use of the app, e.g. tracking distress ratings and times in which they added/removed content, as well as changes in patient outcomes over time, e.g. depression ratings collected as part of the study. In order to facilitate effective communication within the participant's clinical team, information on this portal will be shared among the adolescents' providers within their practice, including the embedded therapist, their primary care provider, and other providers within the office that are designated as part of the adolescents' care team.

6.0 Procedures Involved*

We will develop an app-based intervention, BRITEPath that enhances the capacity of pediatric primary care to effectively manage depressed and suicidal adolescents by referral to embedded MH services. BRITEPath includes three components delivered by MH clinicians, (as described previously in this protocol) including (1.) an electronic on-boarding procedure to that supports MH clinicians, Guide2Brite; (2.) the adolescents' safety planning app, BRITE; and (3.) the clinician dashboard, BRITEBoard, to facilitate treatment planning and communication with other primary care providers. Increasing pediatric primary care's ability to effectively intervene with these mental health problems is likely to lead to reductions in 1) adolescent distress, 2) suicidal and self-harm urges, thoughts, and behaviors, depressive symptoms, and 3) improvements in functioning. Although primary care practices following USPTF recommendations to integrate depression screening and embed MH clinicians into routine care will also inevitably increase detection of depressed and suicidal youth, no effective intervention for the pediatric primary care setting exists to treat and manage these mental health problems. We propose to address this gap in services by developing and pilot testing a novel app-based intervention, BRITEPath, optimized for delivery by embedded MH clinicians to adolescents with depression and suicidality in pediatric primary care.

BRITEPath will include several highly innovative features that are responsive to the needs of both the MH clinician and the adolescent, including (1) brevity of BRITE onboarding (30 minutes); (2) low provider training costs (4 hours); (3) immediate service delivery upon initiation of treatment for depression or suicidality; and (4) provision of services in pediatric primary care clinics where the majority of adolescents are served. Furthermore, the Guide2BRITE component is innovative because, to our knowledge, it is the only safety planning app aimed at helping clinicians deliver an empirically-supported intervention. Guide2BRITE could serve as a paradigm for electronic guides for managing a wide array of mental health problems and emergencies.

This study has the potential to improve treatment outcomes by assisting MH clinicians in creating an individualized safety plan, monitoring symptoms and skills use, and facilitating shared decision making between clinicians and with

PROTOCOL TITLE: The Center for Enhancing Treatment & Utilization for Depression and Emergent Suicidality Phase 1b-Study 3-BRITEPath

parents and patients. The simplicity and flexibility of BRITEPath would allow for its dissemination to reach beyond specialty MH clinics and is consistent with the NIMH 2015 Strategic Plan emphasizing the need for individualized strategies to improve patient outcomes.

It is impractical for MH clinicians to offer BRITEPath only sometimes and to some patients and not others. Although a cluster randomized trial could address this issue, this design is not feasible for a pilot study. Thus, we will utilize a stepped wedge design in which all practices start with Treatment As Usual (TAU) initially and are randomly chosen to transition to BRITEPath at different times. All clinics will be initially monitored for at least two months during TAU for the main outcomes of fidelity to delivery of the intervention. This will be followed by a staggered adoption of BRITEPath. At each time period, a new clinic will begin implementing the intervention. Block randomization determines the order each clinic begins BRITEPath. Each time period (approximately 3 months), a web-based system will be used to assign the next clinic to begin using BRITEPath.

We recognize the limitations of the proposed stepped wedge study design for evaluating the effectiveness of BRITEPath, once a practice enters their intervention phase, assignment to BRITEPath cannot be concealed. This concern is somewhat mitigated by blind follow-up assessors. Alternative study designs (e.g., randomized control trial) pose significant implementation challenges. Clinicians may be hesitant to deliver TAU once the BRITEPath intervention is known, which could lead to study condition contamination (e.g., BRITEPath strategies introduced into TAU condition) and nonrandom patient assignment to condition (e.g., more high acuity patients referred to BRITEPath). In a stepped wedge design these feasibility concerns are addressed by the eventual assignment of all participating practices to the intervention condition and BRITEPath can be offered to all patients moving forward. Additionally, these designs are consistent with our broader goal of enhancing participant and community stakeholder engagement with the ETUDES Center. Results from this pilot trial will allow us to estimate the effect size of the BRITEPath intervention compared to TAU for reducing suicide risk in pediatric primary care. If our initial results show promise, these effect size estimates would be used to design a larger and adequately powered randomized control trial of BRITEPath.

SCREENING

Trained research staff or site staff will determine appropriate potential participants to refer and either refer via email, phone, or in person when staff person is on site. Site staff will review medical record or be made aware of the potential participant's chief complaint at presentation to the clinical setting to determine eligibility. At the time of identifying an eligible participant, trained research staff will complete verbal eligibility screen (with parent if a minor participant is involved or with adult participant). Upon eligibility, trained research site staff will enter participant contact information and date of birth into University of Pittsburgh secure webapp saved behind a firewall. This will create an "ID" which

PROTOCOL TITLE: The Center for Enhancing Treatment & Utilization for Depression and Emergent Suicidality Phase 1b-Study 3-BRITEPath

will communicate with the electronic Guide2Brite to create a profile for the participant in the secure BRITEPath web app.

STUDY INTERVENTION

Following informed consent discussion in the site's clinical setting, trained research clinical staff will implement BRITEPath intervention (described above), help participant download app, and schedule a follow up visit with the participant. Pittsburgh/ETUDES Center research staff will follow up with site clinicians or a designated primary care provider if safety issues emerge during the research phone calls following management of imminent safety/risk.

PITTSBURGH/ETUDES CENTER RESEARCH PHONE CALLS & EMR DATA

During 3 follow research phone calls the measures the research study will collect include: sociodemographic questions, the CSSRS scale & suicide scales, quality of life ratings, treatment history, barriers to treatment, readiness for treatment, attitudes toward seeking psychological help, anxiety & mania adaptive scales via the K-CAT mental health adaptive screen, substance use, depression history, treatment preferences, and if there's a family history of bipolar disorder that impacts the youth's risk for mental health problems. A waiver of HIPAA authorization to collect permission verbally over the phone will be used to access and collect medical record data. Electronic medical record information will be used to supplement treatment and service utilization and uptake of the BRITEPath intervention via the RE-AIM framework described in statistical analysis. Parents will respond to questions about their child, not themselves and youth will answer about themselves. Phone calls will take about 30-60 minutes. Once a participant is completed with the research study follow up period, they will NOT lose access to the BRITE app. They will have access to it as long as they keep it installed on their device.

Only medical information that is necessary to conduct the study intervention will be collected. This will include diagnostic records, referral information, dates, times, outcomes of patient appointments, notes pertaining to patient appointments, who in the EMR prescribed/referred patients to use the intervention, PHQ-9 responses & scores, Service utilization (# visits-PCP, Mental Health specialty, ER, hospitalizations); pharmacotherapy; medical/psychiatric comorbidity; insurance coverage, matching referrals provided by PCP to expert opinion, Use of technical components of interventions & webportals, # of providers engaging in training/intervention, % representation at practice site, # practices who deliver intervention, and any other information needed for cost analysis purposes.

As with the informed consent & assent, it is not practical for researchers to conduct any ETUDES research activities, including the HIPAA authorization for BRITEPath on site due to the time and work flow constraints that emerged from formative qualitative data collection prior to this trial. The providers identified the time constraint of about 5 minutes of patient interaction that would be allowed for

PROTOCOL TITLE: The Center for Enhancing Treatment & Utilization for Depression and Emergent Suicidality Phase 1b-Study 3-BRITEPath

researchers to implement eligibility screening only. Thus the BRITEPath intervention, including informed consent and obtaining any necessary HIPAA authorization, was developed based on pilot focus groups and Phase 1a focus groups & interviews to be implemented without impacting the clinical work flows.

Further, the vast majority of participants recruited across sites are not near the research offices in Pittsburgh. It would put undue burden on the research participants to complete in-person consent, baseline, & follow up assessment visits to ask them to come to instead of using verbal consent in their "real world" setting (especially due to telehealth activities since the COVID-19 pandemic).

A cost analysis is a core piece of the practicality of implementing the BRITEPath intervention within the real world setting of pediatric primary care, thus access to the electronic medical record is required. The intervention being tested as part of the study requires an understanding of the diagnosis, health service utilization, comorbidity, insurance coverage, medication usage, and any other information needed to conduct a cost analysis. The intervention results will include a cost analysis of the service utilization and outcomes of diseases and comorbidity. The results will require information on how many individuals used the intervention and the impact on their service utilization and disease.

Note-full set of data collection measures will be provided upon request. A data use agreement will be developed with site in the event that site investigators plan to collaborate on publications and will have access to de-identified data to conduct analyses. Both the site and Pittsburgh will have access to identifiable data as they are managing participant information/patient records to recruit subjects.

PROCEDURES FOR MANAGING SUICIDAL RISK AT Multi-SITE Location

In the event that an adolescent is not able to commit to a safety plan or if the clinician feels concerned that the patient is at high imminent risk, the clinician will follow their standard care procedures. Standard care involves careful assessment to identify the presence of imminent risk. If the clinician and their supporting clinical team determine the adolescent is in imminent risk, they will communicate the level of risk to the parent/guardian. Additionally, Drs. [name], [name], or [name] will also be available as needed. Depending on the level of clinical severity, the MH clinician has the option to call the phone crisis network either for phone support or to request a mobile crisis team, or to refer the adolescent directly to a local psychiatric emergency to be assessed for inpatient hospitalization.

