17.0 Data Management* and Confidentiality

A stepped wedge design was selected for both ethical considerations and feasibility. A stepped- wedge cluster randomized trial design involves the sequential random rollout of an intervention over multiple time periods following a “baseline” period when no cluster has been exposed. The crossover is typically in one direction, from control to intervention, and continues until all of the clusters receive the intervention with observations taken from every cluster and at each time period. All 3 studies in the ETUDES Center, and specifically, BRITEPath, will utilize this design. Prior to study start, each site will be randomly assigned to switch from.

Treatment As Usual (TAU) to the intervention. In the proposed stepped wedge design, all practices start with TAU (i.e., PCP referral to embedded MH care) and are randomized to transition to implement BRITEPath at different times. All clinics will be initially monitored for at least 2 months during TAU, followed by a staggered adoption of BRITEPath. During each time period, a new clinic will begin to use BRITEPath (order determined by block randomization). A webbased system will randomly assign the next clinic to begin.

With regard to the stated hypothesis: We will perform multilevel modeling to explore time- and intervention-level factors associated with BRITEPath’s use. We will first conduct t-tests for continuous variables and chi-square tests for categorical variables to examine baseline differences in demographic and clinical variables. We will use generalized linear mixed models (nesting for site) to examine between intervention differences in readiness. Distinguishing characteristics will be included as covariates in models examining treatment effects.

Due to the pilot nature of this study, sample size and power considerations center around the precision of confidence interval (CI) width estimation for feasibility outcomes. In this development phase (Aim 1), a sample size of 50 affords us a 95% CI width of no more than 0.28.

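### A TAU comparison is planned, but the written enrolment steps and call timing fit only BRITEPath recipients, and no rule classifies TAU calls made after a clinic crosses over

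*Combined protocol and SAP*

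**What the plan says.** **The comparison.** Hypothesis 1b (section 2.0) contrasts BRITEPath with TAU on depressive symptoms, distress, suicidality and functioning. Impact is to be assessed by "obtaining follow-up phone assessments on suicidality, depression, and functional status at 4 and 12 weeks after intake". Section 6.0 plans an effect-size estimate against TAU and adds: "If our initial results show promise, these effect size estimates would be used to design a larger and adequately powered randomized control trial". Section 17.0 describes a stepped wedge with "observations taken from every cluster and at each time period" and says BRITEPath will use it.

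**The TAU phase.** Section 6.0 states: "All clinics will be initially monitored for at least two months during TAU for the main outcomes of fidelity to delivery of the intervention". The parallel sentence in section 17.0 gives no such outcome: "All clinics will be initially monitored for at least 2 months during TAU, followed by a staggered adoption of BRITEPath". Steps are about three months apart (section 6.0).

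**Enrolment and calls.**
- Screening (6.0) creates an ID that "will communicate with the electronic Guide2Brite to create a profile for the participant in the secure BRITEPath web app".
- After consent, staff deliver BRITEPath (6.0, Study Intervention; 22.0).
- The app is given at the recruitment appointment, and the paid baseline call is placed after the intervention (13.0).
- The research calls come after the intervention (22.0).
- Patients are invited to use the app and take the calls that go with it (26.2).
- The roughly 10 subjects per site are those who have completed consent and the intervention (12.0).

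**Analysis.** Section 17.0 names mixed models nested for site, with covariates. It does not say whether condition is fixed at enrolment or set at each call.

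**The concern.** There are two linked gaps.

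First, a stepped wedge needs outcome data from patients in the control phase. The operational text gives site staff one path, from consent to BRITEPath to calls. A clinic still in its TAU phase has no written instruction for enrolling, counting or calling a patient. The one sentence that gives the TAU phase an outcome names fidelity to an intervention not yet in use there, rather than the patient outcomes of Hypothesis 1b.

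Second, TAU patients' follow-up can run past their clinic's crossover. Without a rule, an analyst could label the same week-12 call TAU (by phase at enrolment) or BRITEPath (by call date), and could make that choice after seeing the data.

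At stake are Hypothesis 1b and the effect size that may be carried into a larger trial. The 75% use criterion (2.0) does not need a TAU contrast.

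**Working it through.** **1. The plan's own figure.** Section 17.0 gives a 95% CI width of no more than 0.28 for N = 50. The Wald width at p = 0.5 is 2 × 1.96 × √(0.25/50) = 0.277, so it reproduces. It is a one-group precision figure and says nothing about the TAU contrast.

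**2. The text side by side.**
- *Implies TAU assessments:* calls timed from intake (2.0); blind follow-up assessors (6.0); a call section not limited by arm (6.0); "All participants assigned to the intervention components will receive each of these 3 components" (5.0), which suggests that some participants are not assigned; a TAU group under risk management (15.0); tests of baseline differences (17.0).
- *Fits BRITEPath recipients only:* screening and intervention steps (6.0), site numbers (12.0), app provision and baseline call (13.0), consent and research calls (22.0), invitation (26.2).

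The first list shows intent. Nothing in it says how a TAU-phase patient is enrolled, counted or called.

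**3. Overlap at one clinic.** Inputs: TAU phase of at least 2 months (6.0, 17.0); calls at weeks 4 and 12 (2.0); 4.348 weeks per month.
- 2 months = 8.70 weeks; 12 weeks = 2.760 months; 4 weeks = 0.920 months.
- With T months of TAU and even accrual (assumed), the share of week-12 TAU calls after crossover is min(1, 2.760/T).
- T = 2: 100%, whatever the accrual pattern. T = 3: 2.760/3 = 92%. T = 5: 55%. T = 8: 35%.
- Week 4 at T = 2: 0.920/2 = 46%.

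**4. Pooled over clinics.** The number of clinics is not stated, so 3 to 6 is an assumption. Crossovers are set at months 2, 5, 8, 11 and so on.

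*TAU accrual running to each crossover.* Even over calendar time: Σ min(T, 2.760)/ΣT. For 3 clinics: (2 + 2.76 + 2.76)/(2 + 5 + 8) = 7.52/15 = 50%. Equal TAU numbers per clinic: (1 + 0.552 + 0.345)/3 = 63%.

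*Enrolment stopping at month 7.* Section 9.0 gives 8/2019 to 2/2020, which is seven months counting both ends. The clinic crossing at month 8 then has only enrolments from month 5.24 to 7 affected: 1.76/7 = 25%. Later clinics have none, since 11 − 2.76 = 8.24 > 7. For 3 clinics: (2 + 2.76 + 1.76)/(2 + 5 + 7) = 6.52/14 = 47%, or (1 + 0.552 + 0.251)/3 = 60%.

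| Clinics | To crossover: calendar / equal n | To month 7: calendar / equal n |
|---|---|---|
| 3 | 50% / 63% | 47% / 60% |
| 4 | 40% / 54% | 31% / 45% |
| 5 | 33% / 47% | 23% / 36% |
| 6 | 28% / 42% | 19% / 30% |

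**The case against.** The strongest reply is that TAU data collection is plainly intended. Blinding the assessors mitigates unconcealed assignment only if they call patients in both conditions, and baseline-difference tests presuppose TAU baselines. This stands. A reader might infer that TAU patients will not be assessed at all, and the documents do not support that. The route is implied but not written out, and several written steps contradict it. The fact sheet and consent script are not in the text available, so the point is limited to the protocol wording.

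A second reply is that the fidelity phrase is a slip. That is probably so, given its absence from section 17.0. It needs correcting but does not show that the outcome was replaced.

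A third is that overlap is not harm. This also stands. A reader might take the shares above as the fraction of the effect lost, but no section says that TAU enrollees are onboarded later. Section 6.0 lists "immediate service delivery upon initiation of treatment for depression or suicidality" as a feature, and section 13.0 recruits from intakes, which points to onboarding at entry. Section 6.0's intention to offer BRITEPath to all patients once a practice has crossed leaves the question open.

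The opposite inference, that there can be no bias if nobody is onboarded later, is not safe either. In arguing against other designs, section 6.0 itself names the leakage of BRITEPath strategies into usual care. A TAU patient still in follow-up with clinicians who have since crossed over could be exposed in that way without the app. Coding condition by call date would also count unexposed TAU patients as BRITEPath.

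**Conclusion.** The point holds as a gap between the planned comparison and the written procedures, and should be corrected. Followed literally, the enrolment steps in sections 6.0, 13.0 and 22.0 and the call timing in 13.0 and 22.0 produce no TAU data for Hypothesis 1b or the effect size. The feasibility criterion is untouched.

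The missing classification rule matters because the plan's own timings allow the overlap. At a clinic crossing at the two-month minimum, all week-12 TAU calls are affected, and this rests on no accrual assumption. The other single-clinic figures assume even accrual. The pooled ranges, about 28–63% or 19–60%, rest on assumed clinic numbers, three-month steps from month 2 and the accrual patterns shown. No dilution figure is claimed. Whether bias arises depends on later onboarding, on contamination without onboarding and on how condition is coded, and the documents settle none of these.

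**What to change.** 1. **Reconcile the procedures with the comparison.** Revise sections 6.0 (TAU monitoring sentence, screening, intervention step), 12.0, 13.0, 22.0 and 26.2 to agree with 2.0 and 17.0. TAU-phase patients should be consented, counted and given the same baseline, week-4 and week-12 calls, without BRITEPath onboarding as a precondition. The TAU phase should be stated to collect the Hypothesis 1b outcomes.
2. **Fix the classification rule.** In the main analysis, define condition by the clinic's phase at enrolment and keep all TAU calls. State whether TAU enrollees may be onboarded after crossover. Add one exposure-coded sensitivity analysis, labelled as-treated.

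**Cost.** This needs protocol wording and one extra analysis. Crossover dates can come from the web-based assignment system (6.0), and first-exposure dates from the app-use tracking (5.0) and record data (6.0) already planned.

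**Downside.** Any contamination stays in the main estimate. The as-treated analysis cannot remove it cleanly, because who is onboarded may depend on acuity. Excluding post-crossover TAU calls instead would discard the shares above, including all week-12 TAU data at a clinic crossing at two months. The plan should also say whether TAU patients count within the 50. If, for illustration, 25 of the 50 received BRITEPath, the worst-case interval width for app use would be 2 × 1.96 × √(0.25/25) = 0.39, not 0.28.
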